## 5.4 Derived variables and data convention

### 5.4.1 Derived variables for diary data

For this study, only the sunlight exposure between 1 hour post sunrise and 1 hour pre-sunset is considered and collected. The following wording is not repeated.

The subjects will record in their diaries for the sunlight exposure periods (start/end time), prodromal symptom periods, and pain periods. The subjects' sunlight exposure start and end times will be compared with their state capital cities sunrise and sunset times. The sunlight exposure time beyond the interval (from 1 hour post sunrise to 1 hour pre-sunset) will be excluded from the analyses unless it is specified in a different way.

The analysis windows are defined in the table below. The nominal day for each week relative to the first dose day will be used. Day1 is the first dose day.

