#### 5.4.1.1 The average daily time to first prodromal symptom associated with exposure to sunlight

The following is the procedure to calculate the average daily time to first prodromal symptom associated with exposure to sunlight.

1. If the sunlight exposure time is beyond the interval (from 1 hour post sunrise to 1 hour pre-sunset), then this time is excluded by comparing the sunrise/sunset time.
2. The time to first prodromal symptom associated with exposure to sunlight in a day is calculated. It is the sum of the sunlight exposure time before the first prodromal symptom occurred in the day. If a subject had sunlight exposure but no prodromal

symptom in a day, the sum of the sunlight exposure time for the day is used as the sunlight exposure time to the first prodromal symptom.

3. A diary day is qualified if the subject had non-zero duration of sunlight exposure in the day.
4. The average daily sunlight exposure time to the first prodromal symptom at a time point (Baseline, Week 2, 4, 6, 8, 10, 12, 14, 16, and 22) is the average of the sunlight exposure time to the first prodromal symptom of qualified days in the corresponding 14-day window. At least 1 day diary data is required for each 14 day window to be qualified for this calculation.
5. The minute is used as the unit for calculation of the duration. The Duration will not be rounded. However, in data presentation for listings, the duration will be rounded to integer. HH:MM can be used when the duration is more than 60 minutes. For tables, the duration will be rounded to integer for minimum and maximum and to one decimal place for mean, SD, median and confidence intervals.

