#### **5.4.1.2 The average daily duration of sunlight exposure without prodromal symptoms**

The following is the procedure to calculate the duration of sunlight exposure without prodromal symptoms. The analysis windows are defined in the table 4.

1. Step 1 in section 5.4.1.1 will be applied.
2. The duration of sunlight exposure without prodromal symptoms in a day is calculated. It is the sum of the duration of sunlight exposure periods deducting the prodromal symptom presenting time covered in each period.
3. Step 3 to 5 in Section 5.4.1.1 will be applied.

The following endpoint is derived when applying the rule above without the step 1.

5.4.1.2.1 The average daily duration of sunlight exposure regardless of time of day without prodromal symptoms

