### **7.15.2 Data Handling of eDiary records**

- (1) If a record has “-0:00” as start/end time, the time will be treated as missing.
- (2) If there is inconsistency between start date and end date of a record for prodromal symptom, the following handling rule will be adapted.
  - If recorded end date is later than start date, the record will be divided per day.
  - If recorded start date is later than end date, the record will not be used for analysis.
- (3) If there are duplicated eDiary records, a record with the latest record time will be used.

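### SAP 7.15.2 rule (2) drops a reversed-date prodromal symptom record but keeps its exposure, so that day's time to first symptom can be too long, up to the full exposure if no other symptom record exists

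*SAP*

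**What the plan says.** The diary holds separate items: "The subjects will record in their diaries for the sunlight exposure periods (start/end time), prodromal symptom periods, and pain periods" (SAP 5.4.1). SAP 7.15.3 shows that a symptom record is linked to an exposure record.

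SAP 7.15.2 rule (2) is limited to symptom records: "If there is inconsistency between start date and end date of a record for prodromal symptom, the following handling rule will be adapted". A record that ends on a later date than it starts is split by day. For the reverse order, "If recorded start date is later than end date, the record will not be used for analysis". The rule does not mention the linked exposure.

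For the primary endpoint, SAP 5.4.1.1 step 2 gives two daily values. On a day with a symptom, "It is the sum of the sunlight exposure time before the first prodromal symptom occurred in the day". On a day with exposure and no symptom, "the sum of the sunlight exposure time for the day is used as the sunlight exposure time to the first prodromal symptom". Step 3 then decides which days count: "A diary day is qualified if the subject had non-zero duration of sunlight exposure in the day". Step 4 averages the qualified days in each 14-day window and accepts a window with one day of diary data.

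For symptom-free duration, SAP 5.4.1.2 says: "It is the sum of the duration of sunlight exposure periods deducting the prodromal symptom presenting time covered in each period". SAP 5.4.1.3 uses the same deduction before dividing by the number of periods.

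**The concern.** A subject who enters a symptom with its dates in the wrong order has still reported a symptom. Rule (2) removes that report and leaves the exposure, and step 2 has no branch for a symptom whose onset is unusable. Taken literally, a date-entry error can turn a symptomatic day into a symptom-free one on the primary endpoint. The deduction in 5.4.1.2 and 5.4.1.3 goes with it. The secondary count of exposure episodes with symptoms may also fall, if it is built from timed records.

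The SAP treats a more serious defect more carefully. Rule (1) of 7.15.2 sets an unusable clock time to missing, and 7.15.3 completes missing or partial symptom dates from neighbouring records. A symptom with no usable date is therefore kept, while one with two dates in the wrong order is lost. No reason is given.

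**Working it through.** The plan gives no figure on this point, and SAP section 6 has no formal sample size calculation, so there is nothing to reproduce. The rules come from SAP 5.4.1.1 steps 2 to 4 and 7.15.2 rule (2). All minutes, shares and rates below are assumptions.

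**1. One day.** With the symptom kept, the value is the exposure before the first onset. With no symptom record, it is the sum of all exposure. Assume a 60-minute exposure with onset at 20 minutes and, where stated, a later 30-minute exposure.

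| Day | Symptom kept | Reversed record dropped |
|---|---|---|
| One exposure, one record | 20 | 60 |
| Two exposures, one record (in the first) | 20 | 60 + 30 = 90 |
| Two exposures, two records (second onset 10 minutes into the second exposure), first dropped | 20 | 60 + 10 = 70 |
| Same, second dropped | 20 | 20 |

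Full-exposure scoring occurs only in the first two rows. In the third the value is too long; in the fourth it is unchanged. It is never shortened.

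**2. One 14-day window.** If the day's only symptom record is lost, the window mean rises by g/k, where g is the exposure in minutes after onset that day and k is the number of qualified days.

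- k = 10: g = 5 gives 0.5 minutes, g = 10 gives 1.0, and g = 70 gives 7.0. The last is a mean of (9 × 20 + 90)/10 = 27 against 20.
- g = 40: 40.0 minutes at k = 1, 13.3 at k = 3, 5.7 at k = 7 and 2.9 at k = 14.

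**3. Average over an arm.** Shift = share of symptom days × reversed rate × g. The low end is 0.20 × 0.005 × 20 = 0.02 minutes. The high end is 0.80 × 0.05 × 90 = 3.6 minutes.

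**4. Difference between arms.** Shift = (active share − placebo share) × reversed rate × g. With 30% symptom days on active, 60% on placebo and g = 40:

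- 1% reversed: −0.30 × 0.01 × 40 = −0.12 minutes.
- 5% reversed: −0.30 × 0.05 × 40 = −0.60 minutes.

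Both run toward no effect. A dropped record in the baseline window raises baseline and so lowers the change score.

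**5. Would removing the day cure it?** Take 10 qualified days: five symptomatic with onset at 20 minutes and five symptom-free at 90. The true mean is 55. One record is reversed.

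- Current rule, symptomatic day 90 minutes long: (4 × 20 + 6 × 90)/10 = 62.
- Day removed: (4 × 20 + 5 × 90)/9 = 530/9 = 58.9, so 3.9 of the 7.0 minutes of error remain.
- Current rule, only 5 minutes outdoors after onset: (4 × 20 + 25 + 5 × 90)/10 = 55.5, which is closer to 55 than removal.

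Removal deletes symptomatic days selectively. It reduces the error when time outdoors after onset is long, and can add to it when that time is short.

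**The case against.** The strongest reply is that the SAP does not say outright that such a day is scored symptom-free. Protocol 6.7.1.1 has subjects record the presence of symptoms for each exposure, as well as their timing. The second branch of step 2 is worded for a day without a symptom, not for a day without a usable record, so a programmer could honour recorded presence. That is a possible reading, but no rule tells the programmer to take it, and step 2 gives no value for such a day. The same argument has more force for the episode count. SAP 7.11.2 gives its model but 5.4.1 gives no derivation, so a count built on presence would be unaffected.

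Other points also stand. The trigger is reversed calendar dates, not reversed times within a day. Protocol 4.7.2 asks subjects to let symptom onset limit their time outside, which makes a long stay after onset less typical, so 70 minutes is a high-end value; later exposures on the same day could still produce it. SAP 7.1 lets the blinded data review add handling rules before lock. That offers a route to a correction, but none is written for this case.

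A reader might infer that the rule favours MT-7117. The documents do not support that. The rule is the same in every arm and applies at baseline too. An arm with more symptomatic days has more days open to the error, and if that arm is placebo the pull is toward no effect.

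**Conclusion.** The point holds as a defect in a written rule. On a literal reading, a reversed-date symptom record disappears while its exposure stays. The primary daily value is then too long if that record was the day's only one or marked its first symptom, and exposure continued after onset. The loss of the deduction in 5.4.1.2 and 5.4.1.3 follows in the same way; a fall in the episode count is possible but not certain.

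It would go too far to say that every affected day is scored symptom-free, or that the treatment effect is inflated. The direction of the net effect on the comparison is undetermined. Its size depends on two quantities that the documents do not give: the rate of reversed dates and the minutes outdoors after onset. Over the assumed ranges the average shift within an arm is 0.02 to 3.6 minutes, and is probably small. A single window with few qualified days is more exposed, because one bad record can set its whole value. This is worth correcting before database lock, but nothing here shows that it would change the trial's conclusion.

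**What to change.** Amend SAP 7.15.2 rule (2) as follows.

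- Keep the fact that a symptom was reported, and count the linked exposure as an episode with symptoms.
- If the recorded start falls within the linked exposure, use it as the onset and complete the end by 7.15.3 rule 1.
- Only if the onset cannot be placed, set the day as not evaluable for 5.4.1.1 to 5.4.1.3. Add a sensitivity analysis that keeps the day, with onset bounded by the start of the linked exposure.
- Report the number of affected records by arm.

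The cost is a few SAP sentences and a programming flag, and the blinded data review is a suitable place to settle it. The downside is that a few days may leave the window average. Because these are symptomatic days, some upward bias remains: less than under the current rule when time outdoors after onset is long, but not in every case. A window with one qualified day could become missing. That is why removal should be the last resort and why the bounded sensitivity analysis is needed.

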### **7.15.3 Data Handling of Dropouts or Missing**

Missing data will not be imputed in the summary at each time point.

For AE start and/or end date missing or partial missing, the AE will be treated as TEAE if it cannot be determined a non-TEAE.

For prodromal symptom start/end date missing or partial missing, complete with the following handling rule;

1. For the end date of prodromal symptom missing or partial, the earliest datetime of following two datetime will be used as the end datetime.
  - Start datetime of next sunlight exposure record
  - 23:59 of the day of linked sunlight exposure record
2. For the start date of prodromal symptom missing or partial, the latest datetime of following three datetime will be used as the end datetime.
  - End datetime of prior sunlight exposure record.
  - End datetime of prior prodrome symptom record
  - 0:00 of the day of linked sunlight exposure record

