6.7 Efficacy Assessments

6.7.1 Primary Efficacy Endpoint

6.7.1.1 Sunlight Exposure Diary

The sunlight exposure diary will be completed on a daily basis from Screening to the follow-up visit by the subjects. An example of the sunlight exposure diary (extract) is presented in Section 14.3 (Appendix 3).

Subjects will record their sunlight exposure time in the sunlight exposure diary. For each sunlight exposure, they will record the presence, duration (onset time of the first symptom and recovery time) and severity of the prodromal symptoms. Pain, its severity and duration (onset time and recovery time) will also be recorded separately in the dedicated part of the diary. The severity of prodromal symptoms and pain will be measured using an 11-point Likert scale ranging from 0 to 10, with 0 indicating no symptom and 10 indicating greatest severity of symptom.

Subjects will be instructed to recognize the following photo-provoked symptoms as prodromal:

- Burning/hotness/heating up
- Tingling
- Itching/scratchy
- Stinging
- Others

Subject responses in the sunlight exposure diary will be used to investigate the primary

efficacy endpoint. The data from the diary will also be used for the secondary and other efficacy assessments.

Further details will be provided in a separate study reference manual, and statistical assessment methods for this study endpoint are described in Section 10.2.2.1.

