Body weight	X		X		X		X		X	X		
Height	X		X		X		X		X	X		
Physical examination d	X		X		X		X		X	X		
Vital signs e	X		X		X		X		X	X		
12-lead ECG			X						X			
Hematology/coagulation, biochemistry & urinalysis f	X		X		X f		X		X	X		
Blood collection for porphyrin and protoporphyrin levels g	X						X		X			
Fitzpatrick skin type assessment	X						X		X			
Pregnancy test h	X		X			X	X		X	X		
PK sampling (blood) i			X			X	X		X			
Blood sampling for PGx b			X									
Pharmacodynamics skin biopsy f			X						X			
Dispensing of study			X			X	X	X	X			

Study Period	Double-blind Treatment										Follow-up
	Screening	Visit 2 (Randomization)	Visit 3 f	Visit 4 f	Visit 5	Visit 6	Visit 7	Visit 8 a (EOT)	Visit 9 o (EOS)		
Visit Number	Visit 1		Week 1	Week 2	Week 4	Week 8	Week 12	Week 16	Week 22		
Study Week	Week -2		Day 8±5	Day 15±5	Day 29±7	Day 57±7	Day 85±7	Day 113±7	Day 155±10		
Study Day ± Window	~Day -14 a	Day 1									
medication					X	X	X	X			
Medication accountability											
Subject Questionnaire for study medication l		X									
PROMIS-57					X	X	X	X	X		
PGIC					X	X	X	X	X		
PGIC 2									X		
Sunlight exposure diaries k	←									→	
Melanin density evaluation		X				X		X	X		
In-clinic sunlight exposure test l		X						X			
Nevi evaluation m		X				X		X	(X)		
Exit interview Questionnaire p									X		
Concomitant medication	←									→	
Adverse events	←									→	

Abbreviations: ECG = electrocardiogram; EOS = end of study; EOT = end of treatment; PGIC = Patient Global Impression of Change; PGx = pharmacogenetics(s); PK = pharmacokinetic; PROMIS = Patient-Reported Outcomes Measurement Information System.

- a A minimum of 7 days of outside exposure data is required prior to randomization.
- b Blood samples will be collected for PGx analysis for those subjects who have specifically given informed consent for optional PGx analysis at Visit 2.
- c Skin biopsy (3 mm x 3 mm punch biopsy) will be performed at Visits 2 and 8 in subjects who have specifically given informed consent for skin biopsy.
- d Complete physical examination will be performed at Visit 1 and an abbreviated physical examination will be performed at all other time points.

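### SAP 7.15.3 rule 2 names the wrong field and leaves 'prior' undefined; read naturally, it puts a missing symptom onset before its own exposure and scores a lower bound as observed

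*SAP*

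**What the plan says.** SAP 7.15.3 has two rules for incomplete prodromal symptom times. Rule 1 fills a missing end with the earlier of two times, one of which is "Start datetime of next sunlight exposure record". Rule 2 deals with a missing start: "For the start date of prodromal symptom missing or partial, the latest datetime of following three datetime will be used as the end datetime". Its three candidates are the end of the prior exposure entry, the end of the prior symptom entry, and "0:00 of the day of linked sunlight exposure record". Neither *prior* nor *linked* is defined.

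The onset feeds the primary endpoint through SAP 5.4.1.1. Step 2 defines the daily value: "It is the sum of the sunlight exposure time before the first prodromal symptom occurred in the day". Step 3 decides which days enter the window mean: "A diary day is qualified if the subject had non-zero duration of sunlight exposure in the day". Step 4 sets the minimum: "At least 1 day diary data is required for each 14 day window to be qualified for this calculation".

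Protocol 6.7.1.1 ties symptom timing to individual exposures: "For each sunlight exposure, they will record the presence, duration (onset time of the first symptom and recovery time". SAP 7.15.2(1) treats certain placeholder clock times in the diary as missing, so some missing times are expected.

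**The concern.** Rule 2 fills a start but names an end. Once that is corrected, the choice of candidates still matters. A symptom linked to an outing would normally be expected to begin during it, yet on the natural reading all three candidates fall before the outing starts. The symptom-free minutes of that outing then vanish from the daily value. Step 3 keeps the day, because qualification depends on exposure and not on the score.

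Two things are at stake. Two programmers who read *prior* differently would get opposite extremes for the same record. And a value that is only a lower bound would enter the primary endpoint as if observed, at baseline and after it.

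No planned analysis would reveal this. The per-protocol and Hodges-Lehmann analyses use the same derived daily values, and the multiple imputation in SAP 7.11.1 fills missing window values, whereas a constructed 0 is not missing.

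**Working it through.** The documents state no figure for this rule, so there is none to reproduce. The clock times below are assumptions chosen to show the mechanics.

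**Step 1: which reading of *prior*.** Rule 1 is the mirror image of rule 2 and uses the *next* exposure, so *prior* most naturally means the one before the linked exposure. Also, if *prior* could mean the linked exposure itself, midnight of that day would normally never be the latest candidate.

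**Step 2: daily value** (5.4.1.1 step 2) = sum over outings of max(0, min(outing end, onset) − outing start).

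| Day | True onset | True value | Rule 2, natural reading | Onset at linked start | Onset at linked end |
|---|---|---|---|---|---|
| One outing 10:00–10:40 | 10:20 | 20 | 0 (onset 0:00) | 0 | 40 |
| One outing 10:00–12:00 | 11:30 | 90 | 0 (onset 0:00) | 0 | 120 |
| Outings 9:00–9:40 and 12:00–14:00, symptom linked to the second | 13:30 | 40 + 90 = 130 | 40 (onset 9:40) | 40 | 40 + 120 = 160 |

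For non-overlapping outings, rule 2 therefore gives the same primary value as assuming onset at the start of the linked exposure. If *prior* includes the linked exposure, the last column applies. If true onset was at or before the exposure start, the rule loses nothing. Records that are not the day's first symptom do not affect the daily value.

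**Step 3: window mean.** One affected day that loses L minutes among k qualified days shifts the subject's mean by −L/k.

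- L = 40: −40/14 = −2.9 min; −40/7 = −5.7 min.
- L = 90: −90/14 = −6.4 min; −90/10 = −9.0 min; −90/7 = −12.9 min.

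The value k = 7 comes from the schedule footnote in SAP 1.2: "A minimum of 7 days of outside exposure data is required prior to randomization". Step 4 permits k = 1, where the whole loss passes through, but that needs a window with a single diary day which is also the affected one.

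**Step 4: arm mean of one window.** Shift = −L × p/k, where p is the share of subjects with one affected day. Assume k = 10 and p from 5% to 50%.

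- L = 10: −10 × 0.05/10 = −0.05 min to −10 × 0.50/10 = −0.5 min.
- L = 90: −90 × 0.05/10 = −0.45 min to −90 × 0.50/10 = −4.5 min.

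**Step 5: direction.** An affected baseline window raises the raw change; an affected post-baseline window lowers it. The MMRM adjusts for baseline, so a baseline error does not carry one-for-one into the adjusted difference. The net direction between arms cannot be derived from the documents.

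**The case against.** The strongest reply is that, once the obvious slip is corrected, rule 2 is a uniform lower-bound convention applied identically in every arm of an exploratory trial. As the table shows, it matches onset at exposure start on the primary endpoint. This stands in part: a lower bound can be a legitimate convention, but it should be chosen openly and bracketed by the other bound.

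The argument about *prior* is also not decisive. The linked exposure's own end could be missing under 7.15.2(1), and midnight would then be a working fallback. That is why the text is ambiguous rather than settled.

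The frequency evidence is thin. Section 7.15.2(1) does not say that symptom onsets in particular go missing, the diary is electronic, and the reference manual that might define linkage is not among the documents.

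Some protection exists. The in-clinic timed test does not use the diary, though it is done only before randomization and at Week 16. Rank-based estimation limits the influence of extreme values. The blinded data review in SAP 7.1 may add handling rules, but it does not commit to correcting this one.

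A reader might infer more than the text supports:

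- *The primary endpoint cannot be computed.* Read literally, onset stays blank, but the word is an evident copying slip and nobody is likely to program it that way.
- *The 0 arises because the linked exposure's start is not among the candidates.* Adding that start gives the same score. The 0 arises because every candidate precedes the exposure.

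**Conclusion.** The point holds. Rule 2 is wrong as written, *prior* is undefined, and no other section resolves either. On the more natural reading, a missing onset for the day's first symptom removes all minutes of the linked exposure, and the day still counts. On the other reading, all of those minutes are kept.

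The size is not known. The illustrative shift of 2.9 to 6.4 minutes in one subject's 14-day mean rests on assumed losses of 40 and 90 minutes on a single day. The larger figures need few qualified days or a large share of affected subjects, and the documents support neither assumption. It would be wrong to infer that the treatment comparison is biased in a particular direction or by a material amount; the effect may be small. The case for correction is that the rule feeds the primary endpoint, permits opposite results for one record, and is easy to settle before unblinding.

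**What to change.** Before unblinding:

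1. In rule 2, replace *end datetime* with *start datetime*, and define *prior* and *linked*.
2. Require the filled onset to lie within the linked exposure, no earlier than its start and no later than its end, and state one rule for where. Run the primary MMRM twice more as bounding sensitivity analyses, with onset at the start and at the end of the linked exposure. Do not make dropping the affected days the main rule: that would remove only symptomatic days.
3. Report the number of affected days by arm and window, including baseline.

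The cost is a wording change, a few lines of derivation code and two extra model runs. The blinded data review is a ready occasion to record it.
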